**Statistical Methods****1. Analysis Sets****(1) Safety Analysis Set**

The Safety Analysis Set is the group of subjects who sign informed consent, receive at least 1 dose of study drug and have at least 1 postdose safety assessment.

**(2) Intent-to-Treat (ITT) Analysis Set**

The ITT Analysis Set is the group of subjects who sign informed consent, receive at least 1 dose of study drug and have at least 1 postdose primary efficacy measurement.

**(3) Modified Intent-to-Treat (mITT) Analysis Set**

The mITT Analysis Set is the subset of the ITT Analysis Set who enter the 4 mg Maintenance Period and have at least 1 postdose primary efficacy measurement in the 26-week Maintenance Period.

**2. Efficacy Analyses****Primary Efficacy Analysis**

The number (percentage) of subjects with POS who achieved seizure-free during the 26-week Maintenance Period of 4 mg and the corresponding 95% confidence interval (CI) will be calculated on the mITT Analysis Set. The primary interest of this study will be to confirm that the 95% lower CI is above the pre-specified threshold (ie, 40%). If subjects experience no seizures during the 4 mg Maintenance Period, those will be regarded as seizure-free in this analysis. Otherwise, subjects will be regarded as non-seizure-free.

**Secondary Efficacy Analyses**

The number (percentage) of subjects with POS who achieved seizure-free during the 26-week Maintenance Period regardless of perampanel dose and the corresponding 95% CI will be calculated on the mITT Analysis Set. To examine if the 95% lower CI exceeds the threshold (ie, 40%) is the key secondary efficacy analysis.

The number (percentage) of subjects in the mITT population with POS who achieved seizure-free during the 52-week treatment (ie, 26-week Maintenance Period and 26-week Extension Phase) and the corresponding 95% confidence interval (CI) will be calculated.

Median time to first seizure onset will be estimated by Kaplan-Meier method. Time to first seizure onset will be defined as the time from the first date of Maintenance Period to the date of first seizure

onset during the Maintenance Period. Subjects who withdraw from the study before first seizure onset will be censored at the time of study discontinuation.

Median time to withdraw from the study will be estimated by Kaplan-Meier method. Time to withdraw from the study will be defined as the time from the first date of Maintenance Period to the date of discontinuation from the study. Subjects who are ongoing at the data cutoff will be censored at the time of data cutoff.

#### Exploratory Efficacy Analyses

The number (percentage) of subjects with POS who achieved seizure-free during the 26-week Maintenance Period and the corresponding 95% confidence interval (CI) will be calculated by types of partial seizure.

The percent change in seizure frequency of POS per 28 days in the Maintenance Period and Extension Phase relative to the Pretreatment Phase will be summarized.

The change in EQ-5D-5L measurements from baseline to each postbaseline visit will be summarized.

### 3. Safety Analyses

All safety analyses will be performed based on the Safety Analysis Set.

The AE verbatim descriptions (investigator terms from the CRF) will be coded to system organ class (SOC) and preferred terms (PT) using the Medical Dictionary for Regulatory Activities (MedDRA). The number (percentage) of subjects with treatment-emergent adverse events (TEAEs) and serious adverse events (SAEs) will be summarized by MedDRA SOC and PT. The incidence of TEAEs will be summarized by severity (mild, moderate, or severe). The TEAEs will be summarized for the Treatment Phase and the entire study period (ie, the Treatment Phase or the Extension Phase). The changes from baseline will be summarized by visit using descriptive statistics for continuous variables (eg, laboratory values, vital sign, weight, and ECG parameter). Categorical variables will be summarized as number (percentage) of subjects by visit.

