| Added the footnote “j” that if a taper is decided based on the judgment of the investigator, dispensing the study drug should be needed at early discontinuation visit   | To correct an error/missing items in table 4 | Section 9.5.2 – Table 4                |
| Added the text “return unused medication” in footnote “c” for when a taper is provided after discontinuation in follow-up phase  | To correct an error/missing items in table 4 | Section 9.5.2 – Table 4                |
| Added the footnote “a” on follow-up phase to indicate that visit to be done within $\pm 7$ days of the schedule  | To correct an error/missing items in table 5 | Section 9.5.2 – Table 5                |
| Added the footnote “g” that if a taper is decided based on the judgment of the investigator, dispensing the study drug should be needed, for early discontinuation visit   | To correct an error/missing items in table 5 | Section 9.5.2 – Table 5                |
| Added the text “Return unused medication is needed.” in the footnote “b”   | To correct an error/missing items in table 5 | Section 9.5.2 – Table 5                |
| Added “Dispense subject diary” at early discontinuation visit  | To correct an error/missing items in table 5 | Section 9.5.2 – Table 5                |
| Revised the text for adverse events, such that a treatment-emergent adverse event (TEAE) is defined as an AE that emerges during time from the first dose of study drug to the last visit or 28 days after the subject’s last dose, whichever comes later. | To correct typographic error                 | Section 9.7.1.8.2 – Adverse events     |
| Removed extra text, such that descriptive statistics for ECG parameters and changes from baseline will be presented by visit   | To correct an error/missing items in table 5 | Section 9.7.1.8.5 – Electrocardiograms |

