#### 9.7.1.8 Safety Analyses

All safety analyses will be performed based on the Safety Analysis Set. Safety data will be summarized using descriptive statistics (eg, n, mean, standard deviation, median, minimum, maximum for continuous variables; n [%] for categorical variables). Safety variables include treatment-emergent adverse events (TEAEs), clinical laboratory parameters, vital signs, weight, and 12-lead ECG results. Study Day 1 for all safety analyses will be defined as the date of the first dose of study drug.

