#### 9.7.1.8.5 ELECTROCARDIOGRAMS

Shift tables will present changes from baseline in ECG interpretation (categorized as normal; abnormal, not clinically significant; and abnormal, clinically significant) by visit.

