5.6.3 Laboratory Values

Laboratory results will be summarized using Système International (SI) units. For all quantitative parameters, the actual value and the change from baseline to end of treatment will be summarized using summary statistics. Qualitative parameters will be summarized by number and percentage of subjects, and changes from baseline to end of treatment will be reported using shift tables. Percentages will be based on the number of subjects with both nonmissing baseline and relevant postbaseline results.

Laboratory test results will be assigned a low/normal/high (LNH) classification according to whether the value is below (L), within (N), or above (H) the laboratory parameter's reference range. The result of LNH classification will be provided in a subject data listing.

“Sponsor’s Grading for Laboratory Values” will be used to identify subjects with Treatment-emergent markedly abnormal laboratory value (TEMAV). The number

(percentage) of subjects with TEMAV (markedly abnormal high/low) will be summarized for overall study period including the Follow-up Phase. The TEMAV will be defined in the [section 8.3](#). TEMAV will also be summarized for the Treatment Phase and the entire study period.

The baseline and end of treatment values for quantitative data will be displayed using Box plot.

Subject data listings will be provided.

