5.6.4 Vital Signs

Summary statistics for vital signs parameters (diastolic and systolic blood pressure, pulse, Respiratory rate, and temperature) and weight, and changes from baseline to end of treatment will be presented.

The baseline and end of treatment values will be displayed using Box plot.

Subject data listings will be provided.

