5.6.5 Electrocardiograms

Shift tables will present changes from baseline to end of treatment in ECG interpretation (categorized as normal; abnormal, not clinically significant; and abnormal, clinically significant).

Subject data listings will be provided.

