7 CHANGES IN THE PLANNED ANALYSES

A summary of all major additions, changes and deletions in the planned analyses described in the protocol will be provided in this section.

There was a major addition.

- Add the description of statistical analysis and data handling if the primary endpoint is successfully achieved according the protocol amendment ([section 3](#)).

There were minor additions, changes and deletions other than the above.

- Summarization of “The percent change in seizure frequency of POS per 28 days” has been changed to per 12 weeks from per 28 days because considering baseline collection period in the clinical study protocol (section 5.1.3 and 5.4.3).
- Summarization of “Treatment Compliance” has been added (section 5.2.6).
- Summarization of “The number (percentage) of subjects with POS who achieved seizure-free during the 52-week treatment of 4 mg (ie, 26-week Maintenance Period of 4 mg and 26-week Extension Phase)” has been added (section 5.4.3).
- Summarization of “The number (percentage) of subjects with POS who achieved seizure-free during the entire study period and the corresponding 95% confidence interval (CI)” has been added (section 5.4.3).
- Summarization of “TEAEs by SOC and PT by period, and by dose” has been added (section 5.6.2).
- Summarization of “TEAEs of special interest” has been added (section 5.6.2).
- Summarization of “the actual value and the change from baseline to each postbaseline visit by visit” has been changed to “the actual value and the change from baseline to end of treatment will be summarized” (section 5.4.3).
- Summarization of “shift tables that compare the baseline LNH classification to the LNH classification at each postbaseline visit” has been deleted (section 5.4.3).
- Summarization of “Summary statistics for vital signs parameters and weight, and changes from baseline will be presented by visit” has been changed to “Summary statistics for vital signs parameters and weight, and changes from baseline to end of treatment will be presented” (section 5.6.4).
- Summarization of “Shift tables will present changes from baseline in ECG interpretation by visit” has been changed to “Shift tables will present changes from baseline to end of treatment in ECG interpretation” (section 5.6.5).
- The cases when the plasma perampanel concentration data will be excluded from the calculation of summary statistics have been added (section 5.5.1).

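### Minor: the synopsis plans change-from-baseline statistics for ECG parameters, but Protocol 9.7.1.8.5 and SAP 5.6.5 specify only a shift table of ECG interpretation, so QTcF has no specified numeric summary

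*Protocol*

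**What the plan says.** Four places in the two documents bear on how ECG data are to be summarised.

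- **Protocol synopsis, Safety Analyses:** "The changes from baseline will be summarized by visit using descriptive statistics for continuous variables (eg, laboratory values, vital sign, weight, and ECG parameter". ECG parameter stands in a list of continuous variables, next to laboratory values, vital signs and weight.
- **Protocol 9.7.1.8:** after promising descriptive statistics for safety data, it adds: "Safety variables include treatment-emergent adverse events (TEAEs), clinical laboratory parameters, vital signs, weight, and 12-lead ECG results".
- **Protocol 9.7.1.8.5 (the ECG section):** "Shift tables will present changes from baseline in ECG interpretation", by visit, in three categories (normal, or abnormal with or without clinical significance). Nothing else is specified.
- **SAP 5.6.5:** "Shift tables will present changes from baseline to end of treatment in ECG interpretation", in the same three categories, plus subject listings.

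SAP section 7 records the move of that table away from "Shift tables will present changes from baseline in ECG interpretation by visit" to end of treatment. It says nothing about statistics for ECG parameters.

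**The concern.** A reader of the synopsis would expect a table of measured ECG values, with change from baseline. Neither the protocol's ECG section nor the SAP's provides one. The interpretation category is a reader's overall judgement of the tracing. It does not show the size of any QTcF change, and a general upward shift that leaves tracings in the same category would not appear in it.

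The protocol treats the measured value as important. QTcF above 450 ms on at least two of three readings excludes a subject (exclusion criterion 10). A reading above 450 ms on treatment triggers two more ECGs (Protocol 9.5.1.5.6). A value above 450 ms together with a rise of more than 60 ms should be considered an adverse event, unless it already belongs to a reported clinical symptom (Protocol 9.5.1.5.1). Protocol 7.2 also plans to set this study's safety data beside those of Study 335 to look for monotherapy signals. As specified, this study would bring no numeric QTcF summary to that comparison. The documents do not say what ECG summaries Study 335 has.

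**Working it through.** No figure in the plan has to be reproduced, so the check is a comparison of text. The inputs are the four continuous items named in the synopsis, traced through the protocol body and the SAP.

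| Item in synopsis | Protocol body | SAP |
|---|---|---|
| Laboratory values | 9.7.1.8.3: value and change, by visit | 5.6.3: value and change to end of treatment, box plots, TEMAV counts |
| Vital signs | 9.7.1.8.4: descriptive statistics and change, by visit | 5.6.4: summary statistics, change to end of treatment, box plots |
| Weight | 9.7.1.8.4: as for vital signs | 5.6.4: as for vital signs |
| ECG parameter | 9.7.1.8.5: interpretation shift table only | 5.6.5: interpretation shift table to end of treatment, listings |

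**Step 1: count.** Three of the four items have an item-specific numeric summary in the SAP, and one does not. For vital signs and weight the SAP even adds a display: "The baseline and end of treatment values will be displayed using Box plot". For laboratory values it counts marked abnormalities by period: "TEMAV will also be summarized for the Treatment Phase and the entire study period". ECG has no counterpart to either.

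**Step 2: where the conflict arises.** SAP 5.6.5 keeps the type of analysis in Protocol 9.7.1.8.5. The conflict therefore lies inside the protocol, between the synopsis (supported by the list in 9.7.1.8) and 9.7.1.8.5. The SAP inherits it.

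**Step 3: whether general wording fills the gap.** SAP 5.6 promises mean, SD, median and range for continuous safety data. SAP 8.3 gives one end-of-treatment value rule for laboratory values, vital signs and ECGs, covering both the Treatment Phase and the entire study. These are the nearest SAP text to a numeric ECG summary. Neither names QTcF or any other interval, and a value rule is equally needed for the categorical shift table. QTcF is not mentioned in the SAP. The only QT reference is the name of a standardised MedDRA query in 5.6.2.

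**Step 4: what is covered by other routes.** A QTcF value that meets the adverse-event rule should reach the adverse-event tables. The special-interest summary in SAP 5.6.2 includes the query for torsade and QT prolongation. Any ECG abnormality the investigator regards as an adverse event is to be reported as one. The listings in SAP 5.6.5 give subject-level ECG data. These routes capture events and individual cases, but they give no distribution of measured QTcF.

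**The case against.** **The removal may have been deliberate.** The revision history has an entry for 9.7.1.8.5: "Removed extra text, such that descriptive statistics for ECG parameters and changes from baseline will be presented by visit". It may mean that ECG statistics were taken out on purpose and that the synopsis phrase is a leftover. The entry is ambiguous and describes superseded text, so it proves neither an error nor an intention. If removal was intended, the current synopsis still needs correcting.

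**The source is slight.** It is one example in a synopsis list, the two dedicated ECG sections agree on the type of analysis, and Protocol 9.7.1 leaves analytical detail to the SAP. This stands as a reason to call the point minor. It does not make the documents agree.

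**The table shells may contain a QTcF table.** They are a separate document (SAP section 11) and are not available. The point is therefore limited to what the SAP specifies.

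**Stronger readings that a reader might infer, and that the documents do not support:**

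- *The SAP silently dropped a planned analysis.* It follows the protocol's ECG section, and section 7 discloses the move to end of treatment. Section 7 is silent only relative to the synopsis.
- *Most ECGs are lost because only end-of-treatment values are tabulated.* That is the disclosed move, applied equally to laboratory values and vital signs, and it is a separate matter from the missing numeric summary.
- *QT effects would go undetected.* The adverse-event rule, the QT query and the listings give partial cover.
- *The adverse-event rule is set too high.* Nothing in this inconsistency bears on where its cut-offs lie.

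**Conclusion.** The point holds as a minor inconsistency with a small gap in the safety summary. The synopsis plans descriptive change statistics for ECG parameters. The sections that specify the ECG analysis give a categorical table only, and the SAP's general wording does not name the missing item. ECG is the one item of four without its own numeric summary.

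No efficacy analysis, sample size or success criterion is affected. With a single arm, a mean QTcF change would be descriptive and could not by itself separate a drug effect from other causes. The conclusion rests on the SAP text alone, since the case report form, dataset specifications and table shells could not be checked.

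**What to change.** In SAP 5.6.5, add descriptive statistics for QTcF: the actual value and the change from baseline to end of treatment, for the Treatment Phase and for the entire study. These are the two end-of-treatment definitions already in SAP 8.1 and 8.3.

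State how multiple readings are reduced to one. Three ECGs are taken at Visit 2, and the last-value baseline rule in SAP 8.1 does not mention triplicates. Later visits have three readings only when QTcF exceeds 450 ms. One workable rule is the mean of the Visit 2 triplicate as baseline, written as an exception to 8.1, with the first reading at each later visit. Using the first reading treats all subjects alike, whereas averaging repeats only for those with a high value would pull those values down selectively.

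Record the addition in SAP section 7, noting that it is to end of treatment and not by visit as in the synopsis. Align Protocol 9.7.1.8.5 with the synopsis at the next amendment.

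A sensible optional addition is the number and percentage of subjects with any post-baseline QTcF above 450 ms, with an increase above 60 ms, and with both. These are the protocol's own cut-offs, but no passage plans such counts.

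The minimum alternative is to delete ECG parameter from the synopsis list. That removes the contradiction but leaves QTcF without a numeric summary.

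The cost is one or two descriptive tables from ECGs already scheduled, with no new procedure, assuming numeric QTcF is in the database.

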### 4. Pharmacokinetic Analysis

The Safety Analysis Set will be used for pharmacokinetic analysis. Summary statistics of plasma perampanel concentrations will be obtained by visit.

#### **Interim Analyses**

No interim analysis is planned for this study.

#### **Sample Size Rationale**

In this study, perampanel will be determined to be efficacious if, in untreated subjects with POS (including secondary generalized seizures), the lower limit of the 95% confidence interval for the seizure-free rate in the 26-week Maintenance Period is above the pre-specified threshold (40%).

Based on the results from research papers of AEDs for mono-therapy ([Chadwick, et al., 1999](#), [Arroyo, et al., 2005](#), [Mikkelsen, et al., 1981](#), [Heller, et al., 1995](#), and [Kaneko, et al., 2015](#)), the expected seizure free rate for other AEDs would be assumed 50.0%. According to [Glauser, et al. \(2013\)](#), the relative difference >20% versus the adequate comparator's efficacy point estimate could be considered non-inferior margin if its 95% lower confidence limit was above this lower acceptable cutoff ([Glauser, et. al., 2013](#)).

Under the assumption that the expected seizure free rate of perampanel in the 26-week Maintenance Period would be 60%, sample size of 72 will provide greater than 90% power that the lower limit of the 95% confidence interval for the seizure free rate in the 26-week Maintenance Period is above 40%. Taking into consideration the drop-out rate in the Titration Period (approximately 10%), 80 subjects need to be as the ITT Analysis Set.

If the number of subjects who achieve seizure-free is above the following criteria, this study can declare to confirm the efficacy of perampanel.

**Seizure free rate and 95% Confidence Interval**

| Target Number of mITT | Minimum Number of Subjects Who Achieve 26-week Seizure-free to Exceed the Pre-specified Threshold | Seizure-free Rate (95% CI) (%)a |
|------------------------------|--|---|
| 71                           | 38   | 53.5 (41.3, 65.5)                                 |
| 72                           | 38   | 52.8 (40.7, 64.7)                                 |
| 73                           | 38   | 52.1 (40.0, 63.9)                                 |
| 74                           | 39   | 52.7 (40.7, 64.4)                                 |
| 75                           | 39   | 52.0 (40.2, 63.7)                                 |
| 76                           | 40   | 52.6 (40.8, 64.2)                                 |
| 77                           | 40   | 51.9 (40.3, 63.5)                                 |
| 78                           | 41   | 52.6 (40.9, 64.0)                                 |
| 79                           | 41   | 51.9 (40.4, 63.3)                                 |
| 80                           | 42   | 52.5 (41.0, 63.8)                                 |
| 81                           | 42   | 51.9 (40.5, 63.1)                                 |

CI = confidence interval, mITT = modified intent-to-treat.

a: 95%CI is based on Clopper-Pearson method.

## 4 LIST OF ABBREVIATIONS AND DEFINITIONS OF TERMS

| Abbreviation | Term   |
|--------------|--|
| AE           | adverse event  |
| AED          | antiepileptic drug   |
| ALP          | alkaline phosphatase   |
| ALT          | alanine aminotransferase                                     |
| AMPA         | $\alpha$ -amino-3-hydroxy-5-methyl-4-isoxazolepropionic acid |
| AST          | aspartate aminotransferase                                   |
| ATC          | anatomical therapeutic chemical                              |
| $\beta$ -hCG | beta-human chorionic gonadotropin                            |
| BMI          | Body mass index  |
| BUN          | blood urea nitrogen  |
| CoA          | certificate(s) of analysis                                   |
| CI           | confidence interval  |
| CNS          | central nervous system                                       |
| CPK          | creatine phosphokinase                                       |
| CRA          | clinical research associate                                  |
| CRF          | case report form   |
| CRO          | contract research organization                               |
| CT           | computed tomography  |
| CYP          | cytochrome P450  |
| EAID         | enzyme inducing antiepileptic drug                           |
| ECG          | electrocardiogram  |
| EEG          | electroencephalogram   |
| EIAED        | enzyme inducing antiepileptic drug                           |
| EQ-5D-5L     | EuroQol 5 Dimensions 5 Levels                                |
| EU           | European Union   |
| GABA         | gamma-aminobutylic acid                                      |
| GCP          | Good Clinical Practice                                       |
| GGT          | gamma-glutamyl transferase                                   |
| ICF          | informed consent form  |
| ICH          | International Council for Harmonisation                      |
| IEC          | independent ethics committee                                 |
| ILAE         | International League Against Epilepsy                        |

| Abbreviation | Term   |
|---------------------|---|
| IRB                 | institutional review board  |
| ITT                 | intent-to-treat   |
| IUPAC               | International Union of Pure and Applied Chemistry                   |
| IUS                 | intrauterine hormone-releasing system                               |
| LC-MS/MS            | liquid chromatography with tandem mass spectrometry                 |
| LLT                 | lowest level term   |
| LNH                 | low/normal/high   |
| MedDRA              | Medical Dictionary for Regulatory Activities                        |
| mITT                | modified intent-to-treat  |
| MRI                 | magnetic resonance imaging  |
| POS                 | partial onset seizure   |
| PT                  | preferred term  |
| QD                  | once daily  |
| QT                  | time from the beginning of the QRS complex to the end of the T wave |
| QTc                 | QT interval corrected for heart rate                                |
| QTcF                | QT interval corrected for heart rate using Fridericia's formula     |
| SAE                 | serious adverse event   |
| SAP                 | statistical analysis plan   |
| SAS                 | Statistical Analysis System   |
| SOC                 | system organ class  |
| SOP                 | standard operating procedure  |
| TEAE                | treatment-emergent adverse event                                    |
| TEMAV               | treatment-emergent markedly abnormal laboratory values              |
| ULN                 | upper limit of normal   |
| VNS                 | vagal nerve stimulation   |
| WHO DD              | World Health Organization Drug Dictionary                           |

